9.3 Reportable Device Issues

- All UADEs and ADEs as defined in section 9.2.1 will be reported on both a device issue form
- and AE form, except for skin reactions from CGM sensor placement or pump infusion set
- placement that do not require pharmacologic treatment.
- Device complaints and device malfunctions will be reported except in the following
- circumstances. These occurrences are expected and will not be reported on a Device Issue Form
- assuming criteria for a UADE or ADE have not been met:
- CGM sensor needing replacement prior to labelled maximum use duration
- Infusion set needing replacement prior to labelled maximum use duration
- CGM tape adherence issues

- Battery lifespan deficiency due to inadequate charging or extensive wireless communication
- Intermittent device component disconnections/communication failures not requiring system replacement or workaround/resolution not specified in user guide/manual.
 - Device issues clearly addressed in the user guide manual that do not require additional troubleshooting
- 1142 User error (as defined in section 9.2.1) will only be reported on a Device Issue form if an AE as
- defined in section 9.2.1 results from the error. In these cases, both a Device Issue form and an
- 1144 Adverse Event form will be completed.

9.4 Timing of Event Reporting

- SAEs possibly related to a study device or study participation and UADEs must be reported by
- the investigator to the Coordinating Center within twenty-four (24) hours of the site becoming
- aware of the event. This can occur via phone or email, or by completion of the online serious
- adverse event form and device issue form if applicable. If the form is not initially completed, it
- should be competed as soon as possible after there is sufficient information to evaluate the event.
- All other reportable ADEs and other reportable AEs should be submitted by completion on the
- online form within seven (7) days of the site becoming aware of the event.
- The Sponsor (or CRO) will notify all participating investigators of any adverse event that is
- serious, related, and unexpected. Notification will be made within ten (10) working days after the
- Sponsor becomes aware of the event.
- Each principal investigator is responsible for reporting serious study-related adverse events and
- abiding by any other reporting requirements of his/her local Institutional Review Board or Ethics
- 1158 Committee and the Central IRB (as applicable). Sites relying on the Central IRB must report all
- serious, related adverse events within seven (7) calendar days (in addition to meeting any local
- 1160 IRB reporting requirements).
- Upon receipt of a qualifying event, the Sponsor will investigate the event to determine if a
- 1162 UADE is confirmed, and if indicated, report the results of the investigation to all overseeing
- 1163 IRBs, and the FDA within ten (10) working days of the Sponsor becoming aware of the UADE
- per 21CFR 812.46(b)(2). The Sponsor in conjunction with the Medical Monitor must determine
- if the UADE presents an unreasonable risk to participants. If so, the Sponsor must ensure that all
- investigations, or parts of investigations presenting that risk, are terminated as soon as possible
- but no later than five (5) working days after the Sponsor makes this determination and no later
- than fifteen (15) working days after first receipt notice of the UADE. The investigator(s) may
- then be required to provide approval or acknowledgment of receipt of that notification and must
- submit to their local IRB as required.
- 1171 The investigators are also required to report, without unjustified delay, all reportable device
- deficiencies, irrespective of whether an adverse event occurred.
- Device malfunctions will be handled by the Sponsor or designee as described below. In the case
- of a CGM transmitter or sensor device malfunction, information will be forwarded to Dexcom by
- the site personnel, to be handled by their complaint management system.

1176

1140

1141

- Where an adverse event is suspected to be related only to the study provided insulin from Novo
- Nordisk, and does not result from a possible interaction with the investigational medical device,
- the investigator or the sponsor are encouraged to report the case to the FDA or competent
- authority. Where made aware of such case, the competent authority should apply the guidance
- provided in the Good Pharmacovigilance Practices Module VI with regard to the management of
- this type of safety report. While reporting the suspected adverse reaction, the relevant
- information regarding the CT (i.e. clinical trial number) or Study ID number must be included in
- the report.

1185 **9.5 Safety Oversight**

- The study Medical Monitor will review all adverse events and adverse device events that are
- reported during the study. SAEs typically will be reviewed within twenty-four (24) hours of
- reporting. Other AEs typically will be reviewed on a weekly basis.
- The Sponsor and Clinical Study Director will be informed of all cases of severe hypoglycemia
- and DKA or HSS and the Medical Monitor's assessment of relationship to the study device; and
- informed of all reported device issues. A Data and Safety Monitoring Board (DSMB) will
- provide safety oversight. The DSMB will be informed of all cases of severe hypoglycemia,
- DKA, and HHS irrespective of device relationship, all device-related SAEs, and all UADEs at
- the time that they occur during the study and will review compiled safety data at periodic
- intervals. The DSMB also will be informed of any ADEs not meeting criteria for a UADE if the
- 1196 Medical Monitor requests the DSMB review. The DSMB can request modifications to the study
- protocol or suspension or outright stoppage of the study if deemed necessary based on the
- totality of safety data available. Details regarding the DSMB's role will be documented in a
- separate DSMB charter.

1200

1201

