9.2.2 Reportable Adverse Events

- 960 For this protocol, a reportable adverse event includes any untoward medical occurrence that 961 meets one of the following criteria:
- 962 1. An SAE as defined in section 9.2.1
- 963 2. An ADE as defined in section 9.2.1, unless excluded from reporting in section 9.3
- 964 3. An AE as defined in 9.2.1 occurring in association with a study procedure
- 965 4. An AE as defined in 9.2.1not related to a device issue which leads to temporary or permanent 966 discontinuation of a study device
- 967 5. An AE as defined in 9.2.1that affects the participant's ability to complete any study 968 procedures
- 969 6. An AE as defined in 9.2.1 for which a visit is made to a hospital emergency department
- 970 7. Hypoglycemia meeting the definition of reportable hypoglycemia in section 9.2.3
- 971 8. Hyperglycemia or ketosis event meeting the criteria defined in section 9.2.4.
- 972 9. An AE as defined in section 9.2.1 considered to be related to either ineffective insulin (e.g., 973 insulin exposed to high temperature that loses potency), signs or symptoms related to insulin 974
- infusion, or changing of type of insulin related to an AE.
- 975 Hypoglycemia and hyperglycemia not meeting the criteria below will not be recorded as adverse
- events unless associated with an Adverse Device Effect or discontinuation of the study device. 976
- 977 Skin reactions from sensor placement are only reportable if severe and/or required treatment.
- 978 All reportable AEs—whether volunteered by the participant, discovered by study personnel
- 979 during questioning, or detected through physical examination, laboratory test, or other means—

will be reported on an AE form online. Each AE form is reviewed by the Medical Monitor to assess safety and to verify the coding and the reporting that is required.

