9.2.3 Hypoglycemic Events

Hypoglycemia is only reportable as an adverse event when one of the following criteria is met:

- A hypoglycemic event occurred meeting the following definition of severe hypoglycemia: the event required assistance of another person due to altered consciousness, and required another person to actively administer carbohydrate, glucagon, or other resuscitative actions. This means that the participant was impaired cognitively to the point that he/she was unable to treat himself/herself independently, was unable to verbalize his/ her needs, was incoherent, disoriented, and/or combative, or experienced seizure or loss of consciousness. These episodes may be associated with sufficient neuroglycopenia to induce seizure or loss of consciousness. If glucose measurements are not available during such an event, neurological recovery attributable to the restoration of glucose to normal is considered sufficient evidence that the event was induced by a low glucose concentration.
- Evaluation or treatment was obtained at a health care provider facility for an acute event involving hypoglycemia, or the participant contacted the site and received guidance following the occurrence of an acute event involving hypoglycemia
- Participant contacted the site because of the occurrence of hypoglycemia
- Hypoglycemia occurred that was associated with an ADE as defined in section 9.2.1
- Study device discontinued due to hypoglycemia

When a severe hypoglycemia event occurs (as defined above), a Hypoglycemia Form should be completed in addition to the Adverse Event Form. Severe hypoglycemia events should be considered to be serious adverse events with respect to reporting requirements. When a severe hypoglycemia event occurs during use of a study device, it generally will be considered to be unrelated to the device (per section 9.2.5) if the device functioned as intended and there does not appear to be a flaw in how the device is intended to function.

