1228 1229 1230 1231 1232 1233 1234 1235	9.6.2 Criteria for Suspending or Stopping Overall Study The DSMB will be immediately notified of all adverse events related to SH, DKA, or HHS, as well as any recurrence of these events across participants or study sites. In addition to the suspension of closed-loop mode use due to a UADE as described above, closed-loop system use could be similarly suspended if the manufacturer of any constituent study device requires stoppage of device use for safety reasons (e.g. product recall). The affected study activities may resume if the underlying problem can be corrected by a protocol or system modification that will not invalidate the results obtained prior to suspension.

1241	Chapter 10: Miscellaneous Considerations
1242	10.1 Drugs Used as Part of the Protocol
1243 1244	Participants using the study pump will use only insulin approved by the FDA for use in the study pump.
1245	10.2 Collection of Medical Conditions and Medications
1246 1247 1248	Pre-Existing Condition: Any medical condition that is either present at screening, a chronic disease, or a prior condition that could impact the participant's health during the course of the study (e.g., prior myocardial infarction or stroke).
1249 1250 1251 1252 1253	Medical Conditions during the study: In addition to conditions meeting the reporting requirements for an adverse event as described in section 9.2.2, the following medical conditions should also be reported: (1) new diagnosis of a chronic disease (i.e., not present at the time of enrollment), and (2) any medical condition that could affect the participant's ability to carry out any aspect of the protocol or could affect an outcome assessment.
1254 1255 1256 1257 1258 1259 1260	Medications: All medication for the treatment of chronic pre-existing conditions, medical conditions (including medical conditions that do not require recording), and/or adverse events that the participant is currently taking at screening and during the course of the study should be recorded. Nutraceuticals and preventative treatment also should be recorded. Medications only taken as needed either be captured with a frequency of "PRN", or can be recorded when used during the study. Glucagon for treatment of severe hypoglycemia will only be recorded if used during the study.
1261	10.3 Prohibited Medications, Devices, Treatments, and Procedures

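### Protocol 9.4 allows seven days to report severe hypoglycemia, DKA or HHS judged unrelated to device and participation, while 9.5 and 9.6.2 promise the DSMB prompt notice of all such events

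*Protocol*

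**What the plan says.** **Site reporting (Protocol 9.4).** The fast route covers two groups, named in the words "SAEs possibly related to a study device or study participation and UADEs must be reported by". For these, the site has 24 hours from its own awareness to inform the Coordinating Center. The remainder is defined by exclusion, in a sentence that opens "All other reportable ADEs and other reportable AEs should be submitted by completion on the". Its time limit reads "online form within seven (7) days of the site becoming aware of the event".

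**What counts as reportable and serious (Protocol 9.2.2 to 9.2.4).** The first item on the list of reportable adverse events is "An SAE as defined in section 9.2.1", with no condition on relatedness. Sections 9.2.3 and 9.2.4 class severe hypoglycemia, DKA and HHS as serious for reporting purposes. Section 9.2.3 adds that when severe hypoglycemia occurs on a study device that worked as intended, "it generally will be considered to be unrelated to the device". Section 9.2.4 says the same of hyperglycemia/DKA events.

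**DSMB notice (Protocol 9.5, 9.6.2 and Protocol Summary).** Section 9.5 has the DSMB informed of all severe hypoglycemia, "DKA, and HHS irrespective of device relationship", when the events occur. Section 9.6.2 is stronger: "The DSMB will be immediately notified of all adverse events related to SH, DKA, or HHS", and it extends this to recurrence across participants or sites. The Protocol Summary promises expeditious reporting of the same events.

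**Medical Monitor (Protocol 9.5, 9.6.1; SAP 14).** SAEs are typically reviewed within 24 hours of being reported. After a single DKA or severe hypoglycemia event, the participant may continue only if the Medical Monitor concurs with the site. SAP section 14 has the Medical Monitor review all severe hypoglycemia and DKA as they occur, whether or not device-related.

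**The concern.** The promise to the DSMB does not depend on relatedness. The site report that must come first does. The Coordinating Center cannot pass on an event it has not received, so for an event judged unrelated the seven-day limit governs how soon the DSMB can know.

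This matters because Protocol 11.11 and SAP 14 provide no formal stopping rules beyond the participant-level and study-level criteria in the protocol. Prompt notice of individual events is therefore an important safeguard. Section 9.6.2 specifically wants recurrence across sites to be seen. With about 20 to 25 sites, no single site can see such a pattern, so detection depends on prompt central reporting. At the level of one participant, the Medical Monitor's concurrence under 9.6.1 also cannot be given before the report arrives.

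**Working it through.** The plan states no figure to reproduce. The check sets the sections side by side and adds their time limits.

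**Step 1. Which limit applies to an unrelated event?** An SAE is a reportable adverse event under 9.2.2 whatever its cause. Section 9.4 gives 24 hours only if it is possibly related to a study device or to participation, or is a UADE. Seriousness alone does not qualify. A severe hypoglycemia, DKA or HHS event judged unrelated on both counts is therefore left in the seven-day group.

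**Step 2. Can such events arise?** Section 9.2.5 treats the possible, probable and definite categories as related, so an event graded unrelated or unlikely related falls outside. Two settings are plausible: the control arm, where participants continue their own insulin delivery with a study CGM, and everyday use of the study pump when it worked as intended. In the second, 9.2.3 and 9.2.4 already point towards a finding of unrelated to the device for severe hypoglycemia and hyperglycemia/DKA. The site must also judge the event unrelated to participation.

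**Step 3. Is there another route?**
- The Medical Monitor has the final say on causality (9.2.5), but can assess an event only after the site has reported it.
- The 24-hour SAE review (9.5) runs from reporting, not from site awareness.
- The dedicated Hypoglycemia and Hyperglycemia/DKA forms (9.2.3, 9.2.4) carry no deadline of their own.

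No section gives a faster site route for these events.

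**Step 4. Permitted delay.**

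| Event | Site to Coordinating Center (9.4) | Plus typical Medical Monitor review (9.5) | Total from site awareness |
|---|---|---|---|
| Possibly related to device or participation, or UADE | 1 day | 1 day | about 2 days |
| Judged unrelated to both | 7 days | 1 day | about 8 days |
| Notice to DSMB under 9.5 and 9.6.2 | – | – | at occurrence, or immediately |

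The difference is 7 − 1 = 6 days at the site step, and the same 8 − 2 = 6 days after review. With the 24-hour limit applied to all three event types, the second row becomes identical to the first.

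**The case against.** **Is 9.4 limited to device-related events?** A reader might infer so. The text also covers SAEs possibly related to study participation, and UADEs. An event must fail both relatedness tests to reach the seven-day limit.

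**Is seven days the default for these events?** A reader might infer this from 9.2.3 and 9.2.4. Their presumption concerns the device only, says nothing about participation, and in 9.2.4 names hyperglycemia/DKA but not HHS. The documents do not make seven days the default.

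**Could a cluster during the unsupervised home challenges go unseen for a week?** That is the setting 9.4 covers best. The challenges are study procedures, so an event tied to one would plausibly count as possibly related to participation and fall under 24 hours. The threshold in 9.2.5 is low: a possible, though weak, scientific basis is enough. Chapter 6 also requires contact with the site within a day of each challenge.

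**Other mitigations.** Seven days is a maximum and sites may report sooner. The concurrence rule in 9.6.1 gives sites a reason to call promptly, though it sets no time limit and does not name HHS. The background section reports no severe hypoglycemia or DKA in the 30-person pilot, so such events may be few. The separate DSMB charter and the site procedures manual were not available and could contain a faster route.

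These points narrow the gap but do not close it. None gives a deadline shorter than seven days for an event judged unrelated to both device and participation, and a faster route in another document would leave the protocol contradicting itself.

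**Conclusion.** The inconsistency is real but limited. Section 9.4 permits up to 7 days from site awareness to the Coordinating Center for severe hypoglycemia, DKA or HHS judged unrelated to both device and participation, or about 8 days with typical Medical Monitor review. Sections 9.5 and 9.6.2 promise the DSMB notice at occurrence or immediately, irrespective of device relationship. The same delay can hold up the concurrence required by 9.6.1 after a single DKA or severe hypoglycemia event.

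The conclusion assumes that 9.4 is applied as written and that a site uses the full limit. How many events would be affected cannot be estimated from the documents. This is a fault in safety reporting and has no bearing on endpoints, analyses or error rates. It is worth correcting because the repair is small and the protocol already commits to the outcome.

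**What to change.** Reconcile 9.4 with 9.5 and 9.6.2 by changing the scope of the 24-hour sentence to:

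*All severe hypoglycemia, DKA and HHS events irrespective of relationship, other SAEs possibly related to a study device or study participation, and UADEs.*

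The seven-day sentence can stand, since it covers whatever remains. The change affects reporting time only. If the charter or procedures manual sets its own time limit, it should be checked against the revised text.

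Cost: one protocol sentence, a memo to sites, and faster reporting of a few events that already require dedicated forms.

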9.6 Stopping Criteria

9.6.1 Participant Discontinuation of Study Device

- 1202 In the case of an unanticipated system malfunction resulting in a severe hypoglycemia or DKA
- event (or a malfunction that could have led to severe hypoglycemia or DKA), use of closed-loop
- mode will be suspended while the problem is diagnosed. The UADE will be reported to the IRB,
- DSMB, and FDA. After assessment of the problem and any correction, use of closed-loop mode
- will not be restarted until approval is received from the IRB, DSMB, and FDA.
- In the absence of a device malfunction, a participant will be discontinued from the study if any of the following occur:
- The investigator believes it is unsafe for the participant to continue on the intervention.

 This could be due to the development of a new medical condition or worsening of an
- 1210 This could be due to the development of a new medical condition of worsening of an 1211 existing condition; or participant behavior contrary to the indications for use of the
- device that imposes on the participant's safety.
- The participant requests that the treatment be stopped
- Participant pregnancy
- Two distinct episodes of DKA, HHS, or severe hypoglycemia as defined in sections 9.2.3 and 9.2.4, respectively.

1217 1218 1219	Each DKA or severe hypoglycemia event will be reviewed by the Medical Monitor with respect to determination of cause and whether the occurrence of the event can be attributed to use of the study device.
1220 1221 1222 1223 1224 1225	An additional requirement for continued study participation following a single DKA or severe hypoglycemia event will be that (1) the site investigator believes that the event is explainable, unlikely to recur, and that it is safe for the participant to continue to use the system and (2) the Medical Monitor concurs. If the Medical Monitor determines that the occurrence of the event indicates that it is not safe for the participant to continue to use the study system, the participant will be discontinued from the study.
1226 1227	Even if the study device system is discontinued, the participant will be encouraged to remain in the study (using CGM only) through the final study visit.
1220	
1228	9.6.2 Criteria for Suspending or Stopping Overall Study
1228 1229 1230 1231 1232 1233 1234 1235	9.6.2 Criteria for Suspending or Stopping Overall Study The DSMB will be immediately notified of all adverse events related to SH, DKA, or HHS, as well as any recurrence of these events across participants or study sites. In addition to the suspension of closed-loop mode use due to a UADE as described above, closed-loop system use could be similarly suspended if the manufacturer of any constituent study device requires stoppage of device use for safety reasons (e.g. product recall). The affected study activities may resume if the underlying problem can be corrected by a protocol or system modification that will not invalidate the results obtained prior to suspension.

1241	Chapter 10: Miscellaneous Considerations
1242	10.1 Drugs Used as Part of the Protocol
1243 1244	Participants using the study pump will use only insulin approved by the FDA for use in the study pump.
1245	10.2 Collection of Medical Conditions and Medications
1246 1247 1248	Pre-Existing Condition: Any medical condition that is either present at screening, a chronic disease, or a prior condition that could impact the participant's health during the course of the study (e.g., prior myocardial infarction or stroke).
1249 1250 1251 1252 1253	Medical Conditions during the study: In addition to conditions meeting the reporting requirements for an adverse event as described in section 9.2.2, the following medical conditions should also be reported: (1) new diagnosis of a chronic disease (i.e., not present at the time of enrollment), and (2) any medical condition that could affect the participant's ability to carry out any aspect of the protocol or could affect an outcome assessment.
1254 1255 1256 1257 1258 1259 1260	Medications: All medication for the treatment of chronic pre-existing conditions, medical conditions (including medical conditions that do not require recording), and/or adverse events that the participant is currently taking at screening and during the course of the study should be recorded. Nutraceuticals and preventative treatment also should be recorded. Medications only taken as needed either be captured with a frequency of "PRN", or can be recorded when used during the study. Glucagon for treatment of severe hypoglycemia will only be recorded if used during the study.
1261	10.3 Prohibited Medications, Devices, Treatments, and Procedures
1262 1263 1264	Only insulins approved for the study pump can be used in the study pump. Afrezza (inhaled insulin) or concurrent use of basal insulin will not be permitted during use of Control-IQ in the trial.
1265	Sulfonylurea use and meglitinide use will not be allowed during the trial.
1266 1267	Addition of glucose-lowering or weight-reduction medications not in use at the time of randomization are prohibited during the 13 weeks of the RCT.
1268 1269	Dose increases in glucose-lowering or weight-reduction medications in use at the time of randomization are not permitted.
1270	Hydroxyurea use is not allowed during the trial, as it may interfere with the study CGM sensor.
1271	Additional medications may be excluded per judgement of the investigator.
1272 1273 1274 1275	The body-worn study devices (study insulin pump, study CGM system) must be removed before Magnetic Resonance Imaging (MRI), Computed Tomography (CT) or diathermy treatment. Participants may continue in the trial after temporarily discontinuing use if requiring one of the treatments above.
1276	10.4 Precautionary Medications, Treatments, and Procedures
1277	Not applicable.

278	10.5 Prophylactic Medications, Treatments, and Procedures
279	Not applicable.
280	10.6 Rescue Medications, Treatments, and Procedures
281 282 283	Participants in the AID group who perform exercise challenges will be expected to have a commercially available glucagon (or glucagon analog) preparation for treatment as needed for severe hypoglycemia. Glucagon will be offered to these participants by the study team.
284	10.7 Pregnancy Reporting
1285 1286 1287	If pregnancy occurs, the participant will be discontinued from the study. The occurrence of pregnancy will be reported to the Sponsor/CRO within seven (7) calendar days and to the Centra IRB on the Unanticipated Problem form within seven (7) calendar days.
288	10.8 Participant Compensation
289	Participant compensation will be specified in the informed consent form.
290	10.9 Participant Withdrawal
291 292	Participation in the study is voluntary, and a participant may withdraw at any time. For participants who withdraw, their data will be used up until the time of withdrawal.
293	10.10 Confidentiality
294 295 296 297	For security and confidentiality purposes, participants will be assigned an identifier that will be used instead of their name. Protected health information gathered for this study will be shared with the coordinating center, the Jaeb Center for Health Research in Tampa, FL. De-identified participant information may also be provided to research sites involved in the study.

1298	Chapter 11: Statistical Considerations
1299	11.1 Statistical and Analytical Plans
1300 1301	The approach to sample size and statistical analyses are summarized below. A detailed Statistical Analysis Plan will be written and finalized prior to the completion of the study.
1302 1303 1304	The primary statistical analyses will involve comparisons of the randomized treatment groups. Additionally, certain single-arm analyses will be conducted on the data collected for the AID group as described in section 11.15.
1305	11.2 Statistical Hypotheses
1306 1307 1308	The primary endpoint for this study is HbA1c at 13-weeks adjusted for baseline HbA1c. The intervention will be considered effective if the AID group is superior to the Control group using a statistical significance of α =0.05.
1309	The null/alternative hypotheses for the primary endpoint are:
1310 1311 1312	 Null Hypothesis: There is no difference in mean HbA1c at 13 weeks between AID and Control Alternative Hypothesis: Mean HbA1c at 13 weeks is different for AID and Control.
1313 1314	Similarly, the null and alternative hypotheses for all of the secondary efficacy endpoints in the hierarchy are:
1315 1316 1317	 Null Hypothesis: There is no difference in the endpoint at 13 weeks between AID and Control Alternative Hypothesis: Endpoint at 13 weeks is different for AID and Control.
1318	11.3 Sample Size
1319 1320 1321 1322	The sample size of 330 randomized participants was selected to provide sufficient exposure to the AID system for regulatory purposes. This equates with a maximum of 220 using the AID system for 13 weeks. Assuming 10% drop out rate in each group, there will be 200 using the system for 13 weeks.
1323 1324 1325 1326 1327 1328	HbA1c data from N=30 participants in the 2IQ pilot study were used to estimate the SD for the power calculation. The SD for baseline values was 1.0%. Assuming a similar SD at follow-up, correlation of 0.3 with baseline, and a two-sided test with type 1 error at 5%, a sample size of N=300 completers will be able to detect an HbA1c difference as small as 0.38% with 90% power. There will be 85% power to detect a difference of 0.35% and 80% power for a difference of 0.33%.
1329	11.4 Efficacy Outcome Measures
1330	11.4.1 Primary Efficacy Endpoint
1331	• HbA1c at 13 weeks (superiority)

1332	11.4.2 Secondary Efficacy Endpoints Included in Hierarchical Analysis
1333 1334	The following secondary endpoints will be tested for superiority, with a hierarchical testing approach to protect the type 1 error rate as described in section 11.13.
1335	• Time in range 70-180 mg/dL
1336	Mean glucose
1337	• Time $> 180 \text{ mg/dL}$
1338	• Time $>$ 250 mg/dL
1339	• CGM-measured prolonged hyperglycemia events (defined in section 11.7.1)
1340	• Time <70 mg/dL
1341	• Time <54 mg/dL
1342	CGM-measured hypoglycemia events (defined in section 11.7.1)
1343	• Coefficient of variation
1344	
1345	11.4.3 Other Secondary Efficacy Endpoints
1346 1347	The following efficacy endpoints are considered exploratory as they are not included in the overall type 1 error rate. All statistical tests are for superiority.
1348	Binary HbA1c Endpoints:
1349	HbA1c <7.0% at 13 weeks
1350	HbA1c <7.0% at 13 weeks in participants with baseline HbA1c >7.5%
1351	HbA1c <7.5% at 13 weeks
1352	HbA1c improvement from baseline to 13 weeks >0.5%
1353	HbA1c improvement from baseline to 13 weeks >1.0%
1354	HbA1c relative improvement from baseline to 13 weeks >10%
1355	HbA1c improvement from baseline to 13 weeks >1.0% or HbA1c <7.0% at 13 weeks
1356	Continuous CGM-Measured Endpoints:
1357	Time in range 70-140 mg/dL
1358	Area over the curve (70 mg/dL)
1359	Low blood glucose index
1360	Time $>$ 300 mg/dL
1361	Area under the curve (180 mg/dL)
1362	High blood glucose index
1363	Binary CGM-Measure Endpoints
1364	Time in range 70-180 mg/dL $>$ 70%
1365	Time in range 70-180 mg/dL improvement from baseline to 13 weeks ≥5%

1366	Time in range 70-180 mg/dL improvement from baseline to 13 weeks \geq 10%
1367	Time $<$ 70 mg/dL $<$ 4%
1368	Time <54 mg/dL $<1\%$
1369	Time in range 70-180 mg/dL $>$ 70% and time $<$ 54 mg/dL $<$ 1%
1370	Other Endpoints (analyzed for superiority as continuous variables):
1371	 Insulin
1372	 Total daily insulin delivery
1373	 Percentage of insulin delivered as basal
1374	Weight change
1375	 Change in lipid levels
1376	Cardiovascular events
1377	• Patient-reported outcome (PRO) measures (see section 8.3)
1378	11.4.4 Safety Endpoints
1379	Severe hypoglycemia
1380	Diabetic ketoacidosis
1381	 Hyperosmolar hyperglycemic syndrome
1382	Other serious adverse events
1383	 Unanticipated adverse device effects
1384	• Hypoglycemia and prolonged hyperglycemia endpoints listed as effectiveness endpoints
1385	• Infusion set failures
1386	Other device malfunctions/device issues
1387	11.5 Analysis Datasets and Sensitivity Analyses
1388 1389 1390 1391	All analyses comparing the AID arm with Control arm will follow intention-to-treatment approach, which means participants will be analyzed in the treatment arm assigned by randomization regardless of actual system use. All randomized participants will be included in the primary analysis and secondary analyses of CGM metrics.
1392 1393	Safety outcomes will be reported for all enrolled participants, irrespective of whether the participant was randomized, or the study was completed.
1394	11.5.1 Per Protocol Analyses
1395 1396 1397	Per-protocol analyses will be performed for primary outcome and secondary hierarchical outcomes only if >5% of participants will be excluded. All of the following criteria must be met for a participant to be included in the per-protocol analyses. The criteria are as follows:
1398	• 13-week visit completed
1399	 No major protocol deviations

Device use: AID group - closed loop mode active for at least 80% of the time over the
 13-week period; control group - CGM use for at least 80% of the time over the
 visit period

